8.1.1 Definition of Adverse Events (AE)

An *adverse event* (AE) is any symptom, sign, illness or experience that develops or worsens in severity during the course of the study. Intercurrent illnesses or injuries should be regarded as adverse events. Abnormal results of diagnostic procedures are considered to be adverse events if the abnormality:

- results in study withdrawal
- is associated with a serious adverse event
- is associated with clinical signs or symptoms
- leads to additional treatment or to further diagnostic tests
- is considered by the investigator to be of clinical significance

8.1.2 Definition of Serious Adverse Events (SAE)

Serious Adverse Event

Adverse events are classified as serious or non-serious. A serious adverse event is any AE that is:

- fatal
- life-threatening
- requires or prolongs hospital stay
- results in persistent or significant disability or incapacity
- a congenital anomaly or birth defect
- an important medical event

Important medical events are those that may not be immediately life threatening, but are clearly of major clinical significance. They may jeopardize the subject, and may require intervention to prevent one of the other serious outcomes noted above. For example, drug overdose or abuse, a seizure that did not result in in-patient hospitalization, or intensive treatment of bronchospasm in an emergency department would typically be considered serious.

All adverse events that do not meet any of the criteria for serious should be regarded as *non-serious adverse events*.

8.1.3 Definition of Unanticipated Problems (UP)

Unanticipated Problems Involving Risk to Subjects or Others

Any incident, experience, or outcome that meets all of the following criteria:

- Unexpected in nature, severity, or frequency (i.e. not described in study-related documents such as the IRB-approved protocol or consent form, the investigators brochure, etc)
- Related or possibly related to participation in the research (i.e. possibly related means there is a reasonable possibility that the incident experience, or outcome may have been caused by the procedures involved in the research)
- Suggests that the research places subjects or others at greater risk of harm (including physical, psychological, economic, or social harm).

This definition could include an unanticipated adverse device effect, any serious adverse effect on health or safety or any life-threatening problem or death caused by, or associated with, a device, if that effect, problem, or death was not previously identified in nature, severity, or degree of incidence in the investigational plan or application (including a supplementary plan or application), or any other unanticipated serious problem associated with a device that relates to the rights, safety, or welfare of subjects (21 CFR 812.3(s)).

CONFIDENTIAL

8.2 Classification of an Adverse Event

8.2.1 Severity of Event

For AEs not included in the protocol defined grading system, the following guidelines will be used to describe severity.

- **Mild** Events require minimal or no treatment and do not interfere with the participant's daily activities.
- **Moderate** Events result in a low level of inconvenience or concern with the therapeutic measures. Moderate events may cause some interference with functioning.
- Severe Events interrupt a participant's usual daily activity and may require systemic drug therapy or other treatment. Severe events are usually potentially life-threatening or incapacitating.

8.2.2 Relationship to BCI

The clinician's assessment of an AE's relationship to BCI is part of the documentation process, but it is not a factor in determining what is or is not reported in the study. If there is any doubt as to whether a clinical observation is an AE, the event should be reported. All AEs must have their relationship to study agent assessed. In a clinical trial, the study product must always be suspect. To help assess, the following guidelines are used.

- **Related** The AE is known to occur with cryoablation, there is a reasonable possibility that the study agent caused the AE, or there is a temporal relationship between the study agent and event. Reasonable possibility means that there is evidence to suggest a causal relationship between the study agent and the AE.
- Not Related There is not a reasonable possibility that BCI caused the event, there is no temporal relationship between the study agent and event onset, or an alternate etiology has been established.

For all collected AEs, the clinician who examines and evaluates the participant will determine the AE's causality based on temporal relationship and his/her clinical judgment. The degree of certainty about causality will be graded using the categories below.

- **Definitely Related** There is clear evidence to suggest a causal relationship, and other possible contributing factors can be ruled out. The clinical event, including an abnormal laboratory test result, occurs in a plausible time relationship to drug administration and cannot be explained by concurrent disease or other drugs or chemicals. The response to withdrawal of the drug (dechallenge) should be clinically plausible. The event must be pharmacologically or phenomenologically definitive, with use of a satisfactory rechallenge procedure if necessary.
- **Probably Related** There is evidence to suggest a causal relationship, and the influence of other factors is unlikely. The clinical event, including an abnormal laboratory test result, occurs within a reasonable time after BCI, is unlikely to be attributed to concurrent disease or other drugs or chemicals.
- **Possibly Related** There is some evidence to suggest a causal relationship (e.g., the event occurred within a reasonable time after BCI). However, other factors may have contributed to the event (e.g., the participant's clinical condition, other concomitant events). Although an AE may rate only as "possibly related" soon after discovery, it can be flagged as requiring more information and later be upgraded to "probably related" or "definitely related," as appropriate.

CONFIDENTIAL

- Unlikely to be related A clinical event, including an abnormal laboratory test result, whose temporal relationship to BCI makes a causal relationship improbable (e.g., the event did not occur within a reasonable time after administration of the trial medication) and in which other drugs or chemicals or underlying disease provides plausible explanations (e.g., the participant's clinical condition, other concomitant treatments).
- Not Related The AE is completely independent of BCI and/or evidence exists that the event is definitely related to another etiology. There must be an alternative, definitive etiology documented by the clinician.

8.2.3 Expectedness

[name] (Assistant Professor, Division of Pulmonary, Critical Care, and Sleep Medicine) will be the study's designated medical monitor who will be responsible for determining whether an AE is expected or unexpected. An AE will be considered unexpected if the nature, severity, or frequency of the event is not consistent with the risk information previously described for the study agent.

8.2.4 Time Period and Frequency for Event Assessment

The occurrence of an AE or SAE may come to the attention of study personnel during study visits and interviews of a study participant presenting for medical care, or upon review by a study monitor. All AEs including local and systemic reactions not meeting the criteria for SAEs will be captured on the appropriate RF. Information to be collected includes event description, time of onset, clinician's assessment of severity, relationship to study product (assessed only by those with the training and authority to make a diagnosis), and time of resolution/stabilization of the event. All AEs occurring while on study must be documented appropriately regardless of relationship. All AEs will be followed to adequate resolution.

Any medical condition that is present at the time that the participant is screened will be considered as baseline and not reported as an AE. However, if the study participant's condition deteriorates at any time during the study, it will be recorded as an AE. UPs will be recorded in the data collection system throughout the study.

Changes in the severity of an AE will be documented to allow an assessment of the duration of the event at each level of severity to be performed. AEs characterized as intermittent require documentation of onset and duration of each episode.

The PI will record all reportable events with start dates occurring any time after informed consent is obtained until 7 (for non-serious AEs) or 30 days (for SAEs) after the last day of study participation. At each study visit, the investigator will inquire about the occurrence of AE/SAEs since the last visit. Events will be followed for outcome information until resolution or stabilization.

All unresolved adverse events should be followed by the investigator until the events are resolved, the subject is lost to follow-up, or the adverse event is otherwise explained. At the last scheduled visit, the investigator should instruct each subject to report any subsequent event(s) that the subject, or the subject's personal physician, believes might reasonably be related to participation in this study. The investigator should notify the study sponsor of any death or adverse event occurring at any time after a subject has discontinued or terminated study participation that may reasonably be related to this study. The sponsor should also be notified if the investigator should become aware of the development of cancer or of a congenital anomaly in a subsequently conceived offspring of a subject that has participated in this study.

8.3 Reporting Procedures

8.3.1 Adverse Event Reporting

Any adverse events or serious adverse events possibly, probably, or definitely related to BCI will be reported in real-time notification by the clinical investigators to the Data and Safety Monitoring Board and Data Coordinating Center. In accordance with 21 CFR 812.150(a)(1), the clinical investigators will also report to the IRB as soon as possible and within 10 working days.

In the event of any unexpected fatal or life-threatening suspected adverse reaction, the Data and Safety Monitoring Board and IRB will be notified as soon as possible and within 2 working days.

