2.3 Potential Risks & Benefits

2.3.1 Known Potential Risks

Potential Risks of Bronchoscopic Cryo-Immunotherapy (BCI)

The radial endobronchial ultrasound probe, which will be used to identify lung tumors in BCI, could potentially cause airway trauma, bleeding, or pneumothorax in rare cases. When lung tumors undergo cryoablation in BCI, potential risks include bleeding, hemoptysis, and pneumothorax. Because BCI does not involve taking any biopsies or removing any lung tissue, the risk of bleeding, hemoptysis, and pneumothorax directly related to this intervention are anticipated to be low. After applying freezing temperatures, rewarming will occur to ensure that the cryoprobe does not remain frozen to the target lung tumor. This will avoid accidentally removing or performing a biopsy on the target tumor, which could cause bleeding, hemoptysis, or pneumothorax. However, if a large pneumothorax occurs and is not properly treated, or if severe bleeding occurs, which is not properly controlled, then these potential complications could theoretically cause severe hypoxemia and be life-threatening. If a pneumothorax occurs, treatment with oxygen and possibly tube thoracostomy, depending on the size of the pneumothorax, will be provided. If significant bleeding or hemoptysis occurs, treatment to stop the bleeding may include applying iced saline, topical epinephrine, or placement of an endobronchial blocker. There may be additional risks of BCI that are currently unforeseeable. We will take all due precautions to determine if a potential participant is at increased risk for any adverse events and to minimize any potential complications in advance of undergoing BCI.

BCI will involve exposure to radiation from fluoroscopy to guide the placement of the probe. The risks of receiving very small doses of radiation are thought to be low. These risks are not actually known. Pregnant women cannot be exposed to radiation. Women of child-bearing age must have a negative pregnancy test before they can have an X-ray and undergo appropriate lead shielding to minimize exposure to reproductive organs.

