Participation in this study will lengthen the overall time of bronchoscopy and exposure to general anesthesia by approximately 15-25 minutes. In rare cases, risks associated with general anesthesia include arrhythmias, heart attack, stroke, and death. All due precautions will be taken to determine if you a potential participant is at increased risk for any of these complications. General anesthesia will be provided by an anesthesiologist throughout the procedure.

Potential Risks of Bronchoalveolar Lavage (BAL)

BAL is a low risk procedure, and sometimes is included as a standard of care component in routine bronchoscopy for lung cancer. BAL will be performed for research purposes in this study. Potential rare risks of bronchoalveolar lavage (BAL) are bronchospasm, airway trauma, bleeding, fever, infection, pneumothorax, and hypoxemia.

Potential Risks of Peripheral Blood Draw

Potential risks of blood draws are localized bruising, redness or swelling at the venipuncture site. This is normally self-limited, requiring no treatment.

Other Potential Risks

Participating in clinical research involving the access to, use, and sharing of health information involves a risk of loss of confidentiality. However, privacy procedures in place and good clinical practice guidelines are followed for the study to minimize risks associated with research procedures and participation. We will do our best to minimize this risk by labeling information and samples with a unique code and securely keeping identifiable information separates from data and samples. Enrollment in this study will have no impact on the standard of care portion of the bronchoscopy. Participation will also not delay you from receiving standard of care lung cancer treatment.

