7.1.2 Standard of Care Study Procedures

Pre-BCI screening:

- Medical history (including cancer and cancer treatment history, co-morbidities, functional status, and social history)
- Medication and treatment history (specifically if patient is on a platelet inhibitor other than aspirin
 or anticoagulant), and if patient has previously or is currently receiving chemotherapy, radiation
 therapy, or immunotherapy.
- Physical examination (vital and full physical exam will be performed by clinical team prior to determining patient's fitness for undergoing bronchoscopy
- Chest CT assessment to evaluate for the presence of a bronchus or airway path leading directly to the peripheral lung tumor
- Screening laboratory evaluation as described in Section 7.2
- Pre-BCI blood collection for immune analysis

During bronchoscopy:

• Bronchoalveolar lavage (BAL) will be performed in two locations, which are the regions of the primary tumor and of the distal portion of the same lung. BAL is a standard of care component of routine bronchoscopy for lung cancer.

CONFIDENTIAL

- If there is no pre-existing biopsy-proven non-small cell lung cancer diagnosis, on-site pathology review of a tissue biopsy obtained during bronchoscopy may be performed, if technically feasible or if the patient does not have high risk features for possible non-small cell lung cancer (see above).
- After the standard-of-care portion of the bronchoscopy is complete, the peripheral tumor will need to be identified by radial EBUS. If the peripheral tumor cannot be identified within 20 minutes, then BCI will not be performed.
- BCI will be performed in eligible candidates

Post-BCI:

- Monitor for any adverse events from day 0 to day 7 Post-BCI blood collection for immune analysis on day 7 ± 3
- Post-BCI blood collection for immune analysis on day 14 ± 3
- Patients who undergo BCI and are found not to have non-small cell lung cancer will be monitored for adverse events from day 0 to day 7 and be followed up at a standard of care pose-bronchoscopy visit within 7 ± 3 days. These patients will not have post-BCI blood collected.

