10.3 Analysis Datasets

All participants who were treated with BCI will be included.

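### Relatedness and the main expedited route name only BCI, so some research-lavage harm misses prompt reporting, and participants searched but not frozen have no scheduled safety contact

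*Combined protocol and SAP*

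**What the plan says.** **Reporting.** Section 8.3.1 sets the main expedited route: "Any adverse events or serious adverse events possibly, probably, or definitely related to BCI will be reported in real-time notification" to the DSMB and the data coordinating center, plus an IRB report within 10 working days.

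**Causality.** Section 8.2.2 is headed as relationship to BCI and has no category for another study procedure. Its lowest grade reads: "The AE is completely independent of BCI and/or evidence exists that the event is definitely related to another etiology". The broader two-way guideline in the same section accepts as related an event where the agent is a reasonable cause, "or there is a temporal relationship between the study agent and event". Section 8.2.2 also states that the causality assessment does not decide what gets reported.

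**Lavage.** Section 2.3.1 says "BAL will be performed for research purposes in this study" and lists its risks, among them bronchospasm, bleeding, infection, pneumothorax and hypoxemia. Section 7.1.1 lists BAL as a study-specific procedure. Section 7.1.2 says instead "BAL is a standard of care component of routine bronchoscopy for lung cancer".

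**EBUS search.** Section 2.3.1 says the probe "could potentially cause airway trauma, bleeding, or pneumothorax in rare cases", and places this under the risks of BCI. Section 2.2 describes the search as a step of BCI, and 4.2.1 makes it part of successful BCI. Section 7.1.2 places it before BCI, and a search that fails after 20 minutes means no BCI.

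**Follow-up and analysis set.** The visits in 7.3.3 are both timed from BCI, and the phone check in 5.7.2 is for those who withdraw after BCI. Section 10.3 reads: "All participants who were treated with BCI will be included".

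**The concern.** The trial adds more than the freeze. A participant may also undergo a two-site lavage and an EBUS search of up to 20 minutes after the clinical part of the bronchoscopy is over. Section 2.3.1 attaches named risks to each. The machinery that turns an adverse event into prompt notification is keyed to BCI alone.

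Two things follow. First, a known type of harm traced to the lavage can be correctly rated not related under 8.2.2 and so never reach the DSMB in real time. Second, a participant whose tumor cannot be found has already had the added procedures, but nothing in the schedule brings study staff back to ask about harm.

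At stake is whether the safety summary of a small first-in-human study covers all the risk that the study itself introduces.

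**Working it through.** The documents state no figure on this point, so the check is a reading of the sections side by side, followed by a rough count of the people affected.

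**Step 1: which routes would catch a lavage harm?** Take an event firmly attributed to BAL, of a kind and severity already described in 2.3.1.

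- *8.3.1, main route.* Needs at least possible relation to BCI. The lowest category of 8.2.2 covers an event with another definite cause. Missed.
- *8.3.1, two-working-day route.* Does not name BCI, but needs an unexpected fatal or life-threatening reaction. Missed.
- *8.1.3 and 8.3.2, unanticipated problems, IRB in 3 days.* Covers research procedures generally, but the event must be unexpected in nature, severity or frequency and also suggest greater risk. An event of expected nature and severity is normally missed.
- *4.2.1 and 8.1, DLT.* The CTCAE item needs relation to BCI. The bleeding and chest-tube items carry no relatedness condition as listed, so they can catch those two harms in a frozen participant. The window runs from BCI, so they do not reach an unfrozen one.
- *8.4, halting.* Death, massive hemoptysis and ARDS stop the study whatever the cause. The grade 3 suspension rule uses a category of the 8.2.2 scale.
- *8.5.1, medical monitor.* Reviews all adverse events regularly and notifies the IRB, but a deadline is given only for DLTs. Scheduled DSMB review is described for subjects undergoing BCI.

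No route guarantees prompt DSMB notice of this event.

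**Step 2: participants searched but not frozen.** Section 8.2.4 records all events from consent, regardless of relationship, and follows them to resolution. It depends on events coming to attention at visits, at interviews during medical care or on monitoring. The scheduled contacts are the day 7 and day 14 visits (7.3.3), the day 0-7 monitoring (7.1.2) and the withdrawal phone check (5.7.2). All are conditional on BCI. Section 7.1.2 has a specific rule for frozen participants who turn out not to have NSCLC, and none for this group. Section 5.1 makes EBUS visualization an inclusion criterion, so they could also be treated as ineligible after the lavage has been done.

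**Step 3: how many?** Inputs: 31 of 38 lesions found by radial EBUS in the feasibility study cited in 2.1; 15 to 24 participants (5.6). Let p be the proportion found and N the number treated.

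- Not found: 1 - 31/38 = 7/38 = 18.4%, exact 95% CI 7.7% to 34.3%.
- Searched = N/p; unfrozen = N/p - N.
- N = 24: 24 × 38/31 = 29.4 searched, 5.4 unfrozen. At the interval limits, 2.0 to 12.5.
- N = 15: 15 × 38/31 = 18.4 searched, 3.4 unfrozen (1.3 to 7.8).
- If the 24 counts people searched, not treated: 24 × 0.184 = 4.4.
- Section 2.1 is unclear on whether one excluded patient is within the 38. A denominator of 37 or 39 gives 16.2% or 20.5% not found, and 4.6 or 6.2 unfrozen per 24 treated.
- Assumed 5% or 10% not found: 24/0.95 = 25.3 and 24/0.90 = 26.7 searched, so 1.3 or 2.7 unfrozen.

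**The case against.** The strongest reply is that the plan has more safeguards than 8.3.1 alone suggests. Three stronger readings are tempting, and the documents support none of them.

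- *A reader might infer that EBUS harm is rated not related.* Sections 2.2, 2.3.1 and 4.2.1 treat the search as part of BCI, and on that reading its harms fall under 8.3.1. Only the sequence in 7.1.2 points the other way. The fair statement is that the status is unclear when no freeze follows.
- *A reader might infer that unfrozen participants have no safety follow-up.* Section 8.2.4 requires recording from consent to 7 days (non-serious) or 30 days (serious) after last participation, and follow-up to resolution. What is missing is a scheduled contact.
- *A reader might infer that they are barred from the safety tables.* Section 10.4.3 promises adverse event tables in a total study population that is not defined. This conflicts with 10.3, so the exclusion is an ambiguity and not a settled rule.

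It is also fair that lavage, search and freeze happen in one session. In a frozen participant the temporal wording in 8.2.2 will make many lavage events at least arguably related, and a severe bronchospasm might count as unexpected in severity and go to the IRB within 3 days. The detection rate comes from lesions under 4 cm, whereas this trial selects on a bronchus sign, so about 5 may be too high.

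All of this narrows the point. It does not supply a route for a lavage harm of expected severity with an established cause, or a planned contact after a failed search.

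**Conclusion.** The point stands in a limited form. As written, 8.2.2 and 8.3.1 leave an adverse event firmly attributed to BAL, and of expected nature and severity, outside real-time DSMB notification and the 10-working-day IRB report. The other routes cover only part of that gap. Participants who have BAL and the search but no freeze have no scheduled safety contact and lie outside the 10.3 set, in tension with 10.4.3.

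The group is small: about 5 per 24 treated if the cited detection rate carries over (2 to 12 across its confidence interval), or 1 to 3 at an assumed 5-10% not found. The lavage gap rests on taking BAL as research, as 2.3.1 and 7.1.1 do and 7.1.2 does not. It does not follow that oversight bodies would never hear of such events, since the medical monitor reviews all of them. This is an inexpensive improvement, and it does not bear on the dose-escalation rule.

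**What to change.** 1. In 8.2.2 and 8.3.1, assess and report relatedness to BCI or to any other study procedure (BAL, EBUS search, added anesthesia time, study blood draw), and record which one is suspected. Leave the DLT definition unchanged.
2. Reconcile three conflicts: 2.3.1 and 7.1.1 with 7.1.2 on whether BAL is research; 2.2, 2.3.1 and 4.2.1 with 7.1.2 on whether the EBUS search is part of BCI; and 8.2.2 with 8.3.1 on whether causality decides what is reported.
3. In 10.3, define a safety set of all consented participants who had any study procedure, use it for the tables in 10.4.3, and show those searched but not frozen separately. Extend the 7-day phone check of 5.7.2 to them.

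The cost is protocol wording, one case report form field, one extra table column and a phone call for a handful of people. The downside is a few more reports to the DSMB and IRB.
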